## RESEARCH DESIGN AND METHODOLOGY

We will perform a prospective, randomized trial with a total of 85 patients. Patients undergoing primary RTSA by Dr. [name] at Beaumont Hospital Royal Oak will be screened for eligibility. After the patient has been consented they will be randomized to one of the following two groups:

1. RTSA with humeral component positioned in 0 degrees of version
2. RTSA with humeral component position in 30 degrees of retroversion

The patient will be blinded to the study group.

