## RANDOMIZATION

The 85 patients enrolled in the study will be randomized in a 1:1 ratio to have their procedure performed either with a humeral component positioned in 0 degrees of version or 30

degrees of retroversion. Randomization assignments will be contained in sequentially numbered, opaque, sealed envelopes, which will be prepared by a statistician in the research institute. After the patient is consented, they will be assigned to a group following the treatment listed in the envelope. Key personnel not collecting data will perform randomization and inform the surgeon of the group in order to keep data collection blinded. The patient will also remain blinded to their assignment. Logs will be maintained by the randomizing personnel.

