## STATISTICAL ANALYSES

### SAMPLE SIZE

We performed a sample size analysis to determine how many patients are needed to be able to detect the minimal clinically important difference in shoulder external/internal rotation, which is between 14° and 22°. We used 80% power and a significance level of 0.05, and based on a review of the literature, we expect a standard deviation between 8° and 18°. Table I illustrates for each effect size, the minimum detectable difference with a standard deviation of 8° and of 18°. Using a sample size of 35 per group (effect size = 0.68), we would be able to detect between 5.4° and 12.2° difference, which will be sufficient to detect a clinically important difference.

**Table I.** Varying effect size and sample size for 80% power and  $\alpha=0.05$ , and the minimum detectable differences with a standard deviation of both 8 and 18.

Effect Size	Total N	n Per Group	Standard Deviation	Minimum Detectable Difference	Standard Deviation	Minimum Detectable Difference
0.55	106	53	18	9.9	8	4.4
0.60	89	45	18	10.8	8	4.8
0.64	80	40	18	11.52	8	5.12
0.65	76	38	18	11.7	8	5.2
0.68	70	35	18	12.2	8	5.4
0.7	66	33	18	12.6	8	5.6
0.75	58	29	18	13.5	8	6
0.8	51	26	18	14.4	8	6.4

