### DATA ANALYSIS

The range-of-motion, strength measures, patient-reported outcomes scores, and patient demographic factors will be compared between the two treatment groups. A table of descriptive summaries by treatment group will be prepared (means and standard deviations if normally distributed, median and range if not normally distributed, counts and percentages for categorical variables). Confidence intervals for the means/medians for each of the two groups will also be computed. The change from baseline as well as the absolute postoperative outcomes measurements will be used for comparison. Before comparing continuous variables, data sets will be assessed for normality using a Shapiro-Wilk Test. For normal data, an independent student's t-test will be used to compare means. A Mann-Whitney Rank Sum Test will be used for data that is ordinal or not normally distributed. The two treatment groups will be compared on categorical variables using the Fisher's Exact test.

Missing data will not be imputed, but the number of data points available at each time point postoperatively will be clearly reported in publications. For all tests, a p-value  $< 0.05$  will be considered statistically significant. A Bonferroni correction will be used to account for repeated measures and control for a Type I error. Graduate-trained engineers will analyze data with SPSS statistical software (SPSS Version 22.0, IBM, Inc).

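### Minor, low-cost safeguard: naming Welch's t-test in place of Student's would protect the error rate if the analysed arms come to differ in both size and spread

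*Combined protocol and SAP*

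**What the plan says.** The Data Analysis section sends continuous outcomes through a Shapiro-Wilk test. If normality is not rejected, "For normal data, an independent student's t-test will be used to compare means". Ordinal or non-normal data go to the Mann-Whitney test. No unequal-variance version of the t-test is named, and no check of equal variances. The same sentence covers rotation, strength and patient-reported scores, both as absolute values and as change from baseline. A Bonferroni correction is added, without a stated divisor.

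Three other statements bear on the point:

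- **Arm sizes at entry:** "The 85 patients enrolled in the study will be randomized in a 1:1 ratio" (Randomization). No blocking is described.
- **Losses:** Enrollment and Consent lets patients leave at any time. Under Data Analysis, "Missing data will not be imputed". Losses therefore pass straight into the numbers analysed.
- **Spread:** in the Sample Size section, "we expect a standard deviation between 8° and 18" degrees. This is one range for the measure, and no SD is given by arm.

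**The concern.** Student's t-test estimates one common variance. When the arms differ in size, the larger arm dominates that estimate, while the smaller arm's mean is the less precisely known. If the smaller arm is also the more variable, the standard error comes out too small and the test rejects too often. If the larger arm is the more variable, the opposite happens.

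External and internal rotation at two years are the primary outcomes. Whether the p-value errs high or low would then depend on which arm lost more patients, and the plan does not control that. Welch's test estimates the same difference in mean degrees without assuming a common variance.

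**Working it through.** **Inputs from the documents.** 85 patients randomised 1:1, so about 43/42. The sample size is 35 per group, 70 in total. The gap is 85 − 70 = 15 patients, 15/85 = 17.6%; no dropout rate is stated. Level 0.05 and power 80%; sidedness is not stated, and two-sided is assumed because it reproduces Table I. SD 8° to 18°.

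**Assumptions.** Normal data; 70 analysed; SD 18° in one arm and 14.4°, 12° or 8° in the other (ratios 1.25, 1.5 and 2.25). These pairs lie inside the plan's range, but the plan does not assign them to arms.

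**1. The plan's own figure.** The Sample Size section says "we would be able to detect between 5.4° and 12.2° difference" with 35 per group. At effect size 0.68, the two-sided equal-variance t-test has power 0.801 with 35 per group. The detectable differences are 0.68 × 18 = 12.2° and 0.68 × 8 = 5.4°. The figure reproduces. Each column of Table I uses one SD for both arms.

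**2. Why size and spread must both differ.** The true variance of the difference in means is σ₁²/n₁ + σ₂²/n₂. The pooled test expects [((n₁−1)σ₁² + (n₂−1)σ₂²)/(n₁+n₂−2)] × (1/n₁ + 1/n₂).

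- 35/35, SD 18 and 8: true (324 + 64)/35 = 11.09; pooled (388/2) × (2/35) = 11.09. They are identical.
- SD 18 in 30 patients, SD 12 in 40: true 324/30 + 144/40 = 14.40; pooled (29×324 + 39×144)/68 × (1/30 + 1/40) = 220.8 × 0.0583 = 12.88. The standard error is too small by a factor √(14.40/12.88) = 1.06.
- SD 18 in 30, SD 8 in 40: true 10.8 + 1.6 = 12.40; pooled 174.9 × 0.0583 = 10.20. Factor √(12.40/10.20) = 1.10.
- SD 18 in 40, SD 8 in 30: true 8.1 + 2.13 = 10.23; pooled 213.1 × 0.0583 = 12.43. The standard error is now too large by a factor √(12.43/10.23) = 1.10.

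**3. Resulting error rates.** Simulation with no true difference, two-sided nominal 5%, 400,000 replicates per cell (simulation error about 0.03 to 0.04 points). Entries are the pooled test's rejection rate in %.

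| n with SD 18 / n in other arm | other SD 14.4 | other SD 12 | other SD 8 |
|---|---|---|---|
| 35/35 | 5.04 | 5.00 | 5.15 |
| 32/38 | 5.47 | 5.86 | 6.60 |
| 30/40 | 5.82 | 6.39 | 7.67 |
| 38/32 | 4.65 | 4.35 | 3.95 |
| 40/30 | 4.36 | 3.92 | 3.21 |

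Welch's test stays between 4.9% and 5.1% in these cells. As a check, the pooled rate was computed without simulation as the average of 2Φ(−c·S√(1/n₁+1/n₂)/√(σ₁²/n₁+σ₂²/n₂)), where S is the pooled SD and c the t critical value, over the two sample variances. It agrees within 0.1 point.

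**4. How likely such splits are.** If arms start at 43/42 and 15 patients are lost at random (hypergeometric), the arm sizes differ by a median of 2 and by 8 at the 95th percentile. A split of 38/32 or worse has probability about 16%, and 40/30 or worse about 1.1%. Averaged over all such splits, the pooled level for the three SD pairs is 5.0% if the more variable arm starts with 43, and 5.1%, 5.2% and 5.4% if it starts with 42. If the envelopes instead held a simple unblocked sequence, 40/30 or worse among 70 patients (binomial, one half) has probability about 28%. The documents do not say which applies.

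**5. Cost of Welch when SDs are equal.** Power at effect size 0.68, Student against Welch: 0.8004 and 0.8002 at 35/35; 0.793 and 0.792 at 40/30; 0.779 and 0.776 at 43/27.

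**6. Under a Bonferroni level.** At an illustrative 0.0125 (four visits, an assumed divisor), 30/40 gives 1.8% against 1.2% for Welch with SD 18 and 12, and 2.4% against 1.3% with SD 18 and 8.

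**The case against.** The strongest case for leaving the text alone is that nothing in the plan points to the conditions that cause trouble. Allocation is 1:1, patients are blinded, and every patient is called as each visit approaches, so there is no stated reason to expect lopsided loss. With random loss from 43/42, a 40/30 split is rare. Inflation and conservatism then largely cancel, so the average level stays near 5%. The t-test is also used only when Shapiro-Wilk does not reject, and the working threshold is set by the Bonferroni correction. Student's test is a conventional choice in a 1:1 trial. All of this stands, and it limits the weight of the point.

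A reader might infer two stronger things. The first is that 8° and 18° are the SDs of the two arms. They are not: the Sample Size section gives one uncertain SD, and Table I applies each value to both arms. The second is that the plan therefore fails to hold its 0.05 level. The documents do not support that either. The departure is conditional on a split and a difference in spread that the plan does not predict.

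The objection does not give a reason to prefer the pooled test. The documents do not exclude unequal spread, describe no blocking and let losses flow into the analysis. The Bonferroni correction lowers the threshold but does not remove the relative distortion.

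**Conclusion.** The point holds as a cheap improvement of minor weight. Given unequal analysed arms and unequal SDs together, the pooled test departs from nominal in either direction. In moderate cases (SD ratio 1.25 to 1.5) this is about 5.5% to 6.4% at 32/38 to 30/40 when the smaller arm is the more variable, and about 3.9% to 4.4% at 30/40 when the larger arm is. With the extreme pair inside the plan's range (18° and 8°), the 30/40 figures are about 7.7% and 3.2%. With equal arms, or with equal SDs, there is nothing to correct.

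These rates rest on normal data, 70 analysed patients, assumed arm-specific SDs and an uncorrected two-sided 0.05. The error rate has not been shown to fail. The case for the change is that the protection costs almost nothing.

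**What to change.** In the Data Analysis section, name Welch's t-test (equal variances not assumed) in place of Student's for every comparison of means, with no preliminary test of equal variances to choose between them. The plan now specifies confidence intervals only for each group separately. If an interval for the between-group mean difference is reported, take it from the same unequal-variance standard error.

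The cost is one sentence and about 0.1 to 0.3 points of power if the SDs are in fact equal. The quantity estimated, the sample size and Table I are unchanged. The edit does not reach the Mann-Whitney branch, which stays as written. It should be made before the data are analysed, so that the choice of test does not depend on the results.

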## OBJECTIVE

- The primary objective of this study is to determine whether external rotation and internal rotation two years postoperatively is impacted by humeral component version in reverse shoulder arthroplasty
- The secondary objective is to determine whether functional outcomes two years postoperatively are impacted by humeral component version in reverse shoulder arthroplasty

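### The two-year rotation test has no baseline covariate and takes nothing from the 3-, 6- and 12-month values; a baseline-adjusted repeated-measures model would be an inexpensive, modest improvement

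*Combined protocol and SAP*

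**What the plan says.** The Objective section asks "whether external rotation and internal rotation two years postoperatively is impacted by humeral component version". Under Data Collection and the Schedule of Events, rotation is measured before surgery and at 3 months, 6 months, one year and two years.

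For continuous outcomes the Data Analysis section gives two tests. If the data look normal, a "t-test will be used to compare means"; otherwise, "A Mann-Whitney Rank Sum Test will be used for data that is ordinal or not normally distributed". Two versions of each outcome are compared: "The change from baseline as well as the absolute postoperative outcomes measurements will be used for comparison". On missing values: "Missing data will not be imputed, but the number of data points available at each time point postoperatively will be clearly reported". Repeated visits are dealt with only through multiplicity: "A Bonferroni correction will be used to account for repeated measures and control for a Type I error".

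No covariate adjustment, longitudinal model or missing-data sensitivity analysis is named. On numbers, the design section says "We will perform a prospective, randomized trial with a total of 85 patients", while Sample Size needs 35 per group. No dropout rate is given.

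**The concern.** A patient examined before surgery and at 3, 6 and 12 months, but not at two years, adds nothing to either two-year comparison. The change score uses the preoperative value by subtraction, which is not the same as adjusting for it, and it needs the same two-year value.

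Two things are at stake. The first is precision: the covariate and the earlier visits carry information that is collected and then left out of the main test. The second is bias: if the patients lost by two years differ in rotation from those who stay, and that relation or the loss rate differs between arms, the two-year difference is distorted. Reporting the counts shows the loss but does not correct for it. Enrolling more than 70 patients protects the number analysed, not the comparability of those who remain.

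**Working it through.** **The plan's own figure.** Inputs from Sample Size: effect size 0.68, 80% power, alpha 0.05, SD 8° to 18°. The normal approximation, 2 × (1.960 + 0.842)² / 0.68², gives 34 per group. The two-sample t-test gives 34.94, so 35, with power 0.801. The detectable differences 0.68 × 8 = 5.4° and 0.68 × 18 = 12.2° agree with Table I. The sample size reproduces.

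**Room for loss.** 1 − 70/85 = 17.6%. This is inferred from the two totals; it is not a stated dropout rate.

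**Assumptions.** 43 vs 42 patients, SD 18°, about 18% loss, correlation with the preoperative value 0.2-0.4, correlation between postoperative visits 0.4-0.6. The documents give none of the correlations and no mechanism of loss.

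**Precision, random loss.** With 35 per group, the SE of the absolute comparison is 18 × √(2/35) = 4.30°. With baseline correlation r, a change score multiplies this by √(2 − 2r), which is 1.265 at 0.2 and 1.095 at 0.4. A baseline covariate multiplies it by √(1 − r²), which is 0.980 and 0.917. Simulation (12,000 replicates) agrees closely. SEs in degrees:

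| Baseline r / visit r | Absolute | Change | Baseline only | Earlier visits only | Both | Both ÷ absolute | Both ÷ change | Both ÷ baseline only |
|---|---|---|---|---|---|---|---|---|
| 0.2 / 0.4 | 4.31 | 5.45 | 4.25 | 4.21 | 4.17 | 0.968 | 0.765 | 0.981 |
| 0.4 / 0.4 | 4.31 | 4.71 | 3.96 | 4.20 | 3.91 | 0.908 | 0.830 | 0.987 |
| 0.2 / 0.6 | 4.27 | 5.41 | 4.21 | 4.09 | 4.03 | 0.944 | 0.745 | 0.957 |
| 0.4 / 0.6 | 4.32 | 4.72 | 3.98 | 4.12 | 3.85 | 0.892 | 0.816 | 0.967 |

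The gain is about 3-11% over the absolute test and 17-25% over the change score. At baseline correlation 0.4 most of the gain over the absolute test comes from the covariate. Once the covariate is in, the earlier visits add about 1-4%. Outside this grid the gain over the absolute test ran from 1.3% (baseline 0.1, visits 0.5, loss spread over visits) to 16.9% (baseline 0.5, visits 0.7, loss after one year).

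The detectable difference at SD 18° moves from 12.2° to between 12.2 × 0.892 = 10.9° and 12.2 × 0.968 = 11.8°. All of these are below 14°.

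**Bias.** Loss follows a logistic function of the stated value. The slope is 1.0 or 1.5 per SD in the one-year and two-year rows, and 1.0 in the decline and preoperative rows. 'One arm' means related loss in one arm and random loss at the same rate in the other. Bias in degrees at SD 18°:

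| Loss depends on | Absolute | Change | Model |
|---|---|---|---|
| One-year value, one arm | 1.2 to 2.2 | 0 to 1.5 | within about 0.1 |
| One-year value, both arms, 25% vs 10% lost | 0.9 to 1.7 | 0 to 1.1 | within 0.1 |
| Unseen two-year value, one arm | 2.7 to 3.8 | 1.7 to 3.0 | 1.5 to 2.9 |
| Unseen two-year value, both arms, 25% vs 10% lost | 2.1 to 2.9 | 1.2 to 2.2 | 1.1 to 2.2 |
| Decline after one year, one arm | 1.2 to 1.6 | not tabulated | 1.5 to 2.0 |
| Preoperative value, one arm (r 0.3 and 0.6) | 0.048 × 18 = 0.9 | −0.107 × 18 = −1.9 | about 0 |
| Nothing related to rotation, 25% vs 10% lost | about 0 | about 0 | about 0 |

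If the lost patients also missed the one-year visit on which their loss depended, the model is off by 0.4-0.7° in the one-arm case. At SD 8° all values shrink by 8/18 = 0.44. In the first row the absolute t-test has a type I error of 5.4-8.7% at a nominal 5%.

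**The case against.** The strongest reply is that little is at risk. Patient and examiner are blinded ("The patient will also remain blinded to their assignment"), patients are called before each visit, and the two-year window is ±4 months. No passage suggests that loss will depend on rotation differently by arm. The plan already has a change-from-baseline comparison, which held its type I error at 4.6-5.7% in the one-arm, one-year case. Ordinary ANCOVA at two years would supply much of the precision gain.

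Most of this stands, and it is why the point is an improvement and not an error. Three things remain:

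- Blinding does not stop patients from responding to how the shoulder works.
- The change score's SE is 9-27% larger than the absolute test's, and the change score has the larger bias when loss depends on the preoperative value.
- ANCOVA alone leaves most of the bias from loss that follows the one-year value. At correlations 0.3 and 0.6 it leaves 0.078 of 0.092 SD, that is 1.4° of 1.7°, because it does not use that visit.

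The model is not better in every case. With both correlations at 0.4 and loss depending on the two-year value in one arm, the change score is less biased (1.7-2.2° against 2.0-2.7°), although total error is smaller for the model (4.4-4.7° against 5.1-5.2°). If that dependence is steep and runs in opposite directions in the two arms, a case no document supports, total error is 6.6° for the model against 6.4° for the change score. The model's own type I error was not simulated, which is a reason to specify small-sample degrees of freedom.

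A reader might infer that the plan ignores preoperative rotation. It does not; what is missing is covariate adjustment. A reader might also infer that unequal loss alone biases the result. Loss unrelated to rotation does not.

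**Conclusion.** The point holds as an inexpensive improvement. The two-year test leaves out a baseline covariate and three postoperative measurements that the trial collects anyway. The earlier values may still be compared at their own visits; they are unused only in the two-year test.

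The size is modest: a 3-11% smaller SE than the absolute test, and removal of a bias of about 1-2° at SD 18° when loss depends on recorded values. Both figures rest on assumed correlations, loss and mechanism, and the precision range would be wider on a wider grid.

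Two stronger readings are not supported. One is that the planned two-year comparison is biased: nothing in the documents shows rotation-related loss that differs by arm, and in the one-arm and unequal-rate cases the bias is at most 3.8° against a smallest important difference of 14°. The other is that a repeated-measures model always reduces bias: that is assured only when loss depends on recorded values. The sample size is sound either way.

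**What to change.** For external and internal rotation in degrees, state the primary analysis along these lines:

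*A mixed model for repeated measures will be fitted to all postoperative visits of randomised patients, with group, visit, group-by-visit, preoperative value and preoperative value-by-visit, an unstructured covariance, and Kenward-Roger or Satterthwaite degrees of freedom. The group contrast at two years is the primary estimate. If the fit fails, a simpler covariance named in advance will be used, and failing that, ANCOVA at two years.*

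Keep the planned t-test or Mann-Whitney test and the change-from-baseline comparison as supporting analyses. Keep Mann-Whitney for internal rotation recorded by anatomical level on the Appendix A form; that comparison still rests on patients with a two-year value.

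Add one short sensitivity analysis. Multiply impute missing two-year rotation from group, preoperative value and earlier visits, and add shifts of 0°, ±7° and ±14° to the imputed values in one arm, in the other arm, and in opposite directions. That is 1 + 3 × 4 = 13 settings per outcome. The 14° limit is the lower end of the plan's important difference. With 18% loss, a 14° shift in one arm moves the contrast by about 0.18 × 14 = 2.5°.

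The cost is wording and slightly more analysis work, with no new visits, data or patients. The model relies on missing at random, which is why the shift analysis is needed. It recovers little for patients lost before 3 months. The scope of the Bonferroni sentence is a separate matter and need not change for this fix.

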## RISKS AND BENEFITS

### POTENTIAL BENEFITS TO SUBJECTS

Patients enrolled in the study may have better range-of-motion or function if one technique proves superior. However, there may be no direct benefit from inclusion in this study. It is hoped that the results of this study will help doctors learn which treatment is most effective for maximizing outcomes after reverse total shoulder arthroplasty.

### POTENTIAL RISKS TO SUBJECTS

The risks of participating in this study include the same risks normally associated with reverse total shoulder arthroplasty surgery whether the patient is in the study or not. Both techniques (30 degrees of humeral component retroversion versus 0 degrees of version) are standard-of-care, based on surgeon preference. There is a chance that patients enrolled in the study may have worse range-of-motion or function if one technique proves inferior. However, this has yet to be proven.

With any procedure, unusual, unexpected or previously unreported side effects may occur. Risks will be assessed throughout the course of the study.

There is also the rare risk of breach of confidentiality. Every effort will be made to maintain patient privacy, however this cannot be guaranteed.

